#### At level of treatment decisions:

The endpoints 10 a i. & ii. and b i. & ii. (3CP) are outcome variables with levels 1 = "yes" and 0 = "no", i.e. binary outcomes. For these endpoints, a mixed logistic regression model will be calculated with the specific binary endpoint as dependent variable, group (intervention vs. control) as fixed effect, region of NHs, respective NH, resident and potential life threatening event (PLE) as nested random intercepts.

The treatment effect is presented as OR with corresponding 95%-CI and p-value. Marginal estimators (proportions of residents at t2) with corresponding 95%-CI are given per treatment group.

The endpoints 10 a iii. & iv. and b iii. & iv. will be analysed descriptively. Absolute and relative frequencies will be reported for the treatment groups.

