- 25. number of EMS transports per 100 residents per last 12 months at t2
- 26. number of general practitioner visits per 100 residents per last 12 months at t2
- 27. number of referrals to specialists per 100 residents per last 12 months at t2
- 28. proportion of residents who received at least 1 antibiotic at t2
- 29. proportion of residents with legal guardian at t2
- 30. quality of life: residents capable of self-rating use WHO-QoL German Version; residents incapable of self-rating use QUALIDEM at t2
- 31. Process parameters measuring the effect of ACP at t2:
  - a. proportion of residents with advance care plans signed by facilitators, and/or physicians and/or representatives
  - b. proportion of residents with durable power of attorney
  - c. proportion of residents with POLST-E
  - d. proportion of residents with any ADs

BEVOR // UKE 2023

- e. proportion of ADs signed by resident
- f. proportion of residents with AD-by proxy
- g. proportion of residents with POLST-E
- 32. Anxiety, depression and trauma among bereaved relatives at t2:
  - a. Scoring on Revised Impact of Event Scale (IES-R): min. 0 pts, max. 88 pts., higher score indicates higher impact (trauma)
  - b. Scoring in German version of Hospital Anxiety and Depression Score (HADS-D): min. 0, max. 14, higher score indicates higher degrees of anxiety and depression

Key secondary endpoints are 9e, 10a ii and 10b ii. This choice is informed by blinded baseline analyses.

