## 2.7 Timing of outcome assessments

The timeline of the BEVOR study is as follows (see Fig. 2 of the study protocol): at the start of the study, data collection is initiated, which corresponds with the baseline measurement (t0). At the end of the run-in phase of the intervention, the 12-month observation phase begins (t1). The end of the observation phase corresponds with the measurement at 12-months follow-up (t2). The run-in phase of the intervention describes the time in which the intervention is established and reaches the residents, the NHs and the regions. It lasts from the time of randomization until t1. The intervention itself continues during the observation period.

The 12 months observation period's data will be collected in one follow up collection (DC1) or, respectively, for DC2 continuously over the entire period, including

- interviews with relatives and nursing home staff of deceased residents,
- four three-monthly sessions to identify all potentially life-threatening events and related treatment decisions for the respective preceding 3 months (3CP data collection including interviews), as appropriate.

The start of the observation phase (t1) is fixed for all study centres at 01.09.2021.

**NH level (DC1):** All outcomes on NH level will be measured at t0, t1 and t2 for the preceding 12 months.

**Resident's level (DC2):** Data collection 2 is performed with residents, their surrogates and/or relatives, and the respective nursing staff and contains three different sections with different time points:

- 1. Framework survey including quality of care survey is conducted at t0 and t2 for the 12 months observation period.
- 2. Care consistency with care preferences (3CP) is assessed at t0 for the preceding 3 months and at t2. Data collection at t2 will be splitted into 4 phases of the 12-months observation period (each covering the preceding 3 months), beginning 3 months after t1, to collect data over the twelve months of observation as accurately as possible. It is ensured that there is no overlap in the survey periods.
- 3. The survey of relatives and staff regarding deceased residents is conducted at t0 and continuously over the 12 months before t2.

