### 5.1.2 Primary Outcome

The primary analysis is performed in the ITT population at NH level. For rate comparison a Poisson regression model is calculated taking into account group (intervention vs control) as independent variable, realized follow-up time as offset, region of NHs and the respective baseline hospitalization rate as covariates. The treatment effect is presented as incidence rate ratio (IRR) with corresponding 95%-Confidence interval (CI) and p-value. Marginal estimators (numbers per 100 residents per past 12 -months observation period (from t1 to t2)) with corresponding 95%-CI are given per treatment group.

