### At NH level:

All secondary endpoints are count data.

For the endpoints 1,2, 4 and 5 c. & d., a Poisson Regression model is calculated with the respective number per 100 residents per past 12 months' observation period (from t1 to t2) as dependent variable, group (intervention vs control) as independent variable, number of occupied bed days as offset and the respective baseline rate and region of NHs as covariates.

The treatment effect is presented as incidence rate ratio (IRR) with corresponding 95%-CI and p-value. Marginal estimators (numbers per 100 residents per past 12 -months observation period (from t1 to t2)) with corresponding 95%-CI are given per treatment group.

For the secondary endpoint 3, the number of residents during the observation period before t2 is used as offset variable. The resulting marginal estimators are numbers per 100 residents.

The secondary endpoints 5 a. & b. and 6-7, 8 a. and 9 a. are measured cross-sectional. For these endpoints, a Poisson Regression model is calculated with the respective number as dependent variable, group (intervention vs. control) as independent variable, number of residents as offset and the respective baseline rate and region of NHs as covariates.

The treatment effect is presented as IRR with corresponding 95%-CI and p-value. Marginal estimators (numbers per 100 residents per past 12 -months observation period (from t1 to t2)) with corresponding 95%-CI are given per treatment group.

The secondary endpoints 8 b. - d. and 9 b. - e. are measured cross-sectional, too, but refer to a predefined subgroup.

For these endpoints, a Poisson Regression model is calculated with the respective number as dependent variable, group (intervention vs control) as independent variable and the respective baseline rate and region of NHs as covariates.

For the endpoints 8 b. - d. the number of ADs and for the endpoints 9 b. - e. the number of POLST-Es are set as offset, respectively.

The treatment effect is presented as IRR with corresponding 95%-CI and p-value. Marginal estimators (number per 100 ADs or 100 POLST-Es per past 12 -months observation period (from t1 to t2)) with corresponding 95%-CI are given per treatment group.

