### At resident level:

All analyses relating to the residents of NHs are performed within a framework of multi-level models.

The secondary endpoints 13. – 17., 19. and 25. – 27. are count data. For these endpoints, a mixed Poisson regression model will be calculated with the corresponding number as dependent variable, realized follow-up time as offset, group (intervention vs. control) as fixed effects, the particular baseline measurement as covariate and region NHs and respective NH as nested random intercepts. The treatment effect is presented as IRR with corresponding 95%-CI and p-value. Marginal estimators (numbers per 100 residents per past 12 -months observation period (from t1 to t2)) with corresponding 95%-CI are given per treatment group.

The secondary endpoints 18., 20. - 24., 28. - 29. and 31 are outcome variables with levels 1 = ``yes'' and 0 = ``no'', i.e. binary outcomes. The secondary endpoint place of death (nursing homes vs. others) is also binary.

For binary outcomes, a mixed logistic regression model will be calculated, taking into account the respective binary outcome as dependent variable, group (intervention vs. control) as fixed effect, the particular baseline measurement as covariate and region of NHs and NH as nested random intercept. The treatment effect is presented as odds ratio (OR) with corresponding 95%-CI and p-value. Marginal estimators (proportions of residents at t2) with corresponding 95%-CI are given per treatment group.

The secondary endpoints 11 a. & b. and 12 are continuous and compared between intervention and control group at t2.

A linear mixed model will be calculated including the respective outcome at t2 as dependent variable, group (intervention vs. control) as fixed effects and region of NHs and NH as nested random intercept.

The treatment effect is presented as mean difference with corresponding 95%-CI and p-value. Marginal estimators with corresponding 95%-CI are given per treatment group.

The secondary outcomes 30. and 32 b. are continuous and compared between intervention and control group as change from baseline at t2.

A linear mixed model will be calculated including change from baseline (t2-t0) as dependent variable, group (intervention vs. control) as fixed effects, the respective baseline value (t0) as covariate and region of NHs and NH as nested random intercept.

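### The models for key secondary endpoints 10a ii and 10b ii leave out the 3CP baseline collected at t0, which costs precision and protection against chance imbalance but does not bias the comparison

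*SAP*

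**What the plan says.** SAP section 5.1.3, under the heading on treatment decisions, specifies a mixed logistic model for 10a i-ii and 10b i-ii with "group (intervention vs. control) as fixed effect, region of NHs, respective NH, resident and potential life threatening event (PLE) as nested random intercepts". Group is the only fixed effect.

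Section 2.7 shows that a baseline exists: "Care consistency with care preferences (3CP) is assessed at t0 for the preceding 3 months and at t2". For follow-up it says: "Data collection at t2 will be splitted into 4 phases of the 12-months observation period (each covering the preceding 3 months". The baseline window is therefore three months and the follow-up window twelve.

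Section 1.2.2 gives the endpoints their rank: "Key secondary endpoints are 9e, 10a ii and 10b ii". It adds that this choice drew on baseline data examined with group hidden.

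Elsewhere the SAP adjusts for baseline:

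- Primary outcome (5.1.2): "region of NHs and the respective baseline hospitalization rate as covariates".
- Home-level endpoints referring to a subgroup, including 9e (5.1.3): "group (intervention vs control) as independent variable and the respective baseline rate and region of NHs as covariates".
- Resident-level binary endpoints (5.1.3): "group (intervention vs. control) as fixed effect, the particular baseline measurement as covariate and region of NHs and NH as nested random intercept".

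The resident-level count and change-score models also carry a baseline value. Apart from endpoint 10, only 11 and 12 go without one: "The secondary endpoints 11 a. & b. and 12 are continuous and compared between intervention and control group at t2".

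**The concern.** Two of the three key secondary endpoints have no baseline adjustment, while 9e and routine endpoints such as general practitioner visits do. The SAP gives no reason.

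A single treatment decision has no earlier value of its own, but the nursing home does. The home is the unit that was randomised, and its t0 proportion of decisions with informed preferences (or informed and honoured preferences) measures the same thing before the intervention.

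With 22 homes per arm, persistent differences between homes can make up a good part of the standard error, and an accidental difference at t0 would pass into the estimate. A covariate added after such a difference has been seen would look post hoc, so the choice belongs in the plan.

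**Working it through.** **Plan's own figures.** Section 2.3: 44 homes × 100 residents = 4,400 enrolled; 3,520 analysed / 44 = 80 per home. These agree with each other. The SAP states no power, intracluster correlation (ICC) or number of decisions for the 3CP endpoints, so no precision figure can be reproduced.

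**Is the gap closed elsewhere?** Section 5.2 adds an adjusted analysis, but only for listed factors that differ at p < 0.05. Neither the home-level nor the resident-level list contains baseline 3CP. The region intercept and the stratified randomisation (2.2) deal with differences between regions, not between homes within a region.

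**Chance imbalance.** With 22 homes per arm, the arm difference in a home-level baseline has SD √(2/22) = 0.30 home-level SDs. Under a normal approximation:

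- P(difference beyond ±0.25 SD) = 2 × [1 − Φ(0.25/0.3015)] = 41%
- P(difference beyond ±0.5 SD) = 2 × [1 − Φ(0.5/0.3015)] = 9.7%

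Both ignore stratification, which lowers them.

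**Precision.** Let r be the correlation between observed home-level values at t0 and follow-up. It is an assumption. In a linear approximation, adjustment multiplies the variance of the group effect by 1 − r².

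The covariate costs one degree of freedom. With eight regions (2.1: four centres with two each), 44 − 8 − 1 = 35 degrees of freedom remain before adjustment. The expected inflation is 1 + 1/(35 − 2) = 34/33 = 1.03.

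The last column assumes that the unadjusted model would have 80% power at two-sided 5%. It is Φ(2.802/√(net factor) − 1.960).

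| r | 1 − r² | net factor, × 34/33 | power instead of 80% |
|---|---|---|---|
| 0.2 | 0.96 | 0.99 | 80% |
| 0.3 | 0.91 | 0.94 | 82% |
| 0.5 | 0.75 | 0.77 | 89% |
| 0.6 | 0.64 | 0.66 | 93% |

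Break-even is at r² = 1/34, that is r = 0.17.

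**Which r is plausible?** Write r = CAC × √(R0 × R1), where R = m × ICC / (1 + (m − 1) × ICC) is the reliability of a home's value based on m decisions, and CAC is the correlation of true home effects over time. All inputs are assumptions: ICC 0.05 to 0.20, 5 to 20 decisions per home at t0, four times as many at follow-up (twelve months against three), CAC 0.5 to 0.8. The resident and event levels are folded into the ICC.

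- Low end (ICC 0.05, 5 and 20 decisions, CAC 0.5): R0 = 0.208, R1 = 0.513, r = 0.16; variance factor 0.97, net 1.00.
- High end (ICC 0.20, 20 and 80 decisions, CAC 0.8): R0 = 0.833, R1 = 0.952, r = 0.71; variance factor 0.49, net 0.51.

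**The case against.** The strongest reply is that nothing here is an error. Randomisation makes the unadjusted comparison valid, and the SAP does not contradict itself. Its resident-level models adjust for a resident's own earlier value; a decision has none, and many residents will have had no life-threatening event in the three months before t0. A home-level aggregate would be a new construct among the resident-cohort models. This stands as a plausible reason for the omission, but the SAP does not state it. It rules out a resident-level covariate, not a home-level one, and the home-level models already adjust for the home's own baseline rate.

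The gain may also be small. A three-month window gives a noisy covariate, a run-in phase lies between t0 and the observation year, and the SAP itself treats the pandemic as an outside influence over time (5.4.2). This stands too: at r of about 0.2, the lost degree of freedom takes back most of the benefit.

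A reader might infer more than the SAP supports:

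- **That every home has a usable t0 value.** Section 2.7 says only that 3CP is assessed at t0, and section 3.2 foresees data collection that could not take place.
- **That chance imbalance is likely.** A difference beyond 0.5 SD has probability 9.7% even without allowing for stratification.
- **That the gain equals a fixed number of extra homes.** At r = 0.3, 0.5 and 0.6, 1/(1 − r²) gives 10%, 33% and 56% more homes, but only if r refers to observed home values or if all variance lies between homes. If r refers to true home effects and half the variance lies between homes, 1/(1 − 0.5r²) gives 5%, 14% and 22%.
- **That endpoints 11 and 12 are an equal case.** Different deceased residents are surveyed at t0 and t2, and neither endpoint is key secondary.

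**Conclusion.** The point holds as a missed, inexpensive improvement to two of the three key secondary analyses. Baseline 3CP is collected, nearly all other models use their baseline, and neither the main nor the sensitivity analyses use this one.

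The direction of the precision effect is clear once r exceeds about 0.17. Its size is not: over r = 0.2 to 0.6 the net variance factor runs from 0.99 to 0.66. This rests on an assumed r, a linear approximation to a logistic mixed model, and about 35 home-level degrees of freedom.

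It would be wrong to conclude that the planned estimates are biased or invalid; in expectation they are not. The primary conclusion is untouched, and all secondary analyses are exploratory without multiplicity adjustment (3.1, 5.1.3). The change is advisable, not essential.

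**What to change.** Before unblinding, amend section 5.1.3 for 10a i-ii and 10b i-ii:

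1. Add the home's t0 3CP proportion for the same endpoint as a fixed covariate.
2. Fix one form, for example the empirical logit.
3. State the rule for homes without t0 decisions, for example the overall mean, and say whether homes without any t0 collection are treated the same way.
4. Report the model as now written as a sensitivity analysis.

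Home-level t0 means for endpoints 11 and 12 are optional.

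The cost is one degree of freedom per model (about 3% of variance), a covariate that is noisy because it covers three months, and the need to settle items 2 and 3 in advance. No further data collection is required.

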### At resident level:

All analyses relating to the residents of NHs are performed within a framework of multi-level models.

The secondary endpoints 13. – 17., 19. and 25. – 27. are count data. For these endpoints, a mixed Poisson regression model will be calculated with the corresponding number as dependent variable, realized follow-up time as offset, group (intervention vs. control) as fixed effects, the particular baseline measurement as covariate and region NHs and respective NH as nested random intercepts. The treatment effect is presented as IRR with corresponding 95%-CI and p-value. Marginal estimators (numbers per 100 residents per past 12 -months observation period (from t1 to t2)) with corresponding 95%-CI are given per treatment group.

The secondary endpoints 18., 20. - 24., 28. - 29. and 31 are outcome variables with levels 1 = ``yes'' and 0 = ``no'', i.e. binary outcomes. The secondary endpoint place of death (nursing homes vs. others) is also binary.

For binary outcomes, a mixed logistic regression model will be calculated, taking into account the respective binary outcome as dependent variable, group (intervention vs. control) as fixed effect, the particular baseline measurement as covariate and region of NHs and NH as nested random intercept. The treatment effect is presented as odds ratio (OR) with corresponding 95%-CI and p-value. Marginal estimators (proportions of residents at t2) with corresponding 95%-CI are given per treatment group.

The secondary endpoints 11 a. & b. and 12 are continuous and compared between intervention and control group at t2.

A linear mixed model will be calculated including the respective outcome at t2 as dependent variable, group (intervention vs. control) as fixed effects and region of NHs and NH as nested random intercept.

The treatment effect is presented as mean difference with corresponding 95%-CI and p-value. Marginal estimators with corresponding 95%-CI are given per treatment group.

The secondary outcomes 30. and 32 b. are continuous and compared between intervention and control group as change from baseline at t2.

A linear mixed model will be calculated including change from baseline (t2-t0) as dependent variable, group (intervention vs. control) as fixed effects, the respective baseline value (t0) as covariate and region of NHs and NH as nested random intercept.

The treatment effect is presented as mean difference with corresponding 95%-CI and p-value. Marginal estimators (mean change from baseline at t2) with corresponding 95%-CI are given per treatment group.

Outcome 30 is analyzed stratified by the residents' self-rating capability:

- for residents capable of self-rating the WHO-QoL German Version is used
- for residents incapable of self-rating the QUALIDEM score is used

The secondary outcome 32 a. is evaluated in two different ways. The resulting total score is analysed within the framework of a linear mixed model with the change from baseline as dependent variable, as described above. Additionally, a mixed logistic regression model based on the binary variable suspected post-traumatic stress disorder (yes vs. no) determined by X > 0 vs.  $X \le 0$  is calculated, as described above.

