## b. AND honored:

- i. "ostensible" preferences (independent of any underlying SDM process) were honored (yes vs. no)
- ii. "informed" preferences (at least the 2nd step of the SDM process was reached) were honored (yes vs. no)
- iii. "enabled" preferences (at least the 3rd step of the predefined 4-step SDM process was reached) were honored (yes vs. no)
- iv. "empowered" preferences (at least the 4th step of the predefined 4-step SDM process was reached) were honored (yes vs. no),

continuously over the 12 months before t2.

- 11. Perception of care consistency in residents deceased during the observation period measured as judgement (Likert Scale 0-10) of
  - a. proxies and

- b. nurses, respectively, whether medical care (F2a) and nursing care (F2b) delivered in the past 3 months before death was consistent with the residents' then care preferences, measured by key items F2a/F2b selected from the After Death Bereaved Family Member Interview (ADBI) and documented continuously over the 12 months before t2.
- 12. Shared decision making and Advance Care Planning in residents deceased during the observation period, observed in the 3 months prior to death, and measured by means of the corresponding sections of an adapted German version of the After Death Bereaved Family Member Interview (ADBI):
  - a. Inform and promote shared decision making (problem score #2)
  - b. Encourage advance care planning (problem score #3)
  - c. Overall Rating Scale for patient focused, family centered care
- 13. number of hospitalizations per 100 residents per last 12 months at t2
- 14. number of total hospital days per 100 residents per last 12 months at t2
- 15. number of visits at hospital outpatient services per 100 residents per last 12 months at t2
- 16. number of attempted CPRs in hospital or EMS per 100 residents per last 12 months at t2
- 17. number of intensive care unit days per 100 residents per last 12 months at t2
- 18. proportion of residents with artificial ventilation in hospital or EMS at t2
- 19. number of invasive ventilation hours in hospital per 100 residents per last 12 months at t2
- 20. proportion of residents with PEG in place at t2
- 21. proportion of residents with newly inserted PEG at t2
- 22. proportion of residents with PEG in use at t2
- 23. mortality rate during the observation period before t2
- 24. place of death (nursing home vs. others) during the observation period before t2

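### Invasive ventilation hours (endpoint 19), and to a lesser degree ICU days (17): the random-intercept Poisson model can report a rate ratio far from the ratio of hours or days

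*SAP*

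**What the plan says.** SAP 1.2.2 defines endpoint 17 as "number of intensive care unit days per 100 residents per last 12 months at t2" and endpoint 19 as "number of invasive ventilation hours in hospital per 100 residents per last 12 months at t2". Both are accumulated durations.

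SAP 5.1.3 (At resident level) groups them with event counts: "The secondary endpoints 13. – 17., 19. and 25. – 27. are count data". One model serves the whole group: "a mixed Poisson regression model will be calculated with the corresponding number as dependent variable, realized follow-up time as offset", with group as a fixed effect and "the particular baseline measurement as covariate and region NHs and respective NH as nested random intercepts". Two outputs are promised: "The treatment effect is presented as IRR with corresponding 95%-CI and p-value", and "Marginal estimators (numbers per 100 residents per past 12 -months observation period (from t1 to t2)) with corresponding 95%-CI are given per treatment group".

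This model has no resident-level random term, dispersion parameter or robust variance. The negative binomial check in SAP 5.2 covers the primary endpoint only. For the 3CP endpoints (5.1.3, At level of treatment decisions) the SAP does add resident and event intercepts, so their absence here is specific to this model.

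**The concern.** A Poisson model with an NH intercept suits events that occur roughly one at a time. Ventilation hours do not: one resident may add 70 hours or more to a home's total, while many homes total zero. Without a resident-level variance term, this spread can only go into the home intercept, which standard software takes as normal on the log scale. Its SD grows far beyond any real difference between homes. The group coefficient is then a log-scale contrast dominated by which homes are at zero, and it no longer has to equal the ratio of hours.

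At stake are the two outputs that the SAP promises for endpoints measuring intensive treatment, in a trial whose stated goal is fewer unwanted interventions. A reader will take the IRR as the relative change in hours or days, and the group figures as hours or days per 100 residents.

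**Working it through.** **Inputs from the SAP.** 22 homes and 1,760 residents analysed per arm (2.3), so 1,760 / 22 = 80 per home. Model and outputs as in 5.1.3. The SAP gives no rate, duration or variance for 17 or 19, so there is no planned figure to reproduce.

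**Assumptions (not in the SAP).**
- Set A: ventilation in 0.5-2% of residents per year, mean 72 h, CV 1.5; ICU use mainly 1.5-5%, mean 4 days where stated. The main run used a true between-home log-SD of 0.2.
- Set B: ventilation 1.5%, mean 120 h, CV 1.5; ICU use 5%, mean 6 days, CV 1.2; between-home log-SD 0.3.

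Without resident covariates, the likelihood of a Poisson model with an NH intercept depends only on home totals. It was fitted by adaptive quadrature without the baseline covariate or region intercept, with 60 to 600 runs per scenario.

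**Step 1: homes at zero.** P(home total = 0) ≈ exp(−80 × user rate), ignoring true between-home variation. Users are halved in the intervention arm.

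| Endpoint, control rate | Users per home, control / intervention | Homes at zero, control / intervention |
|---|---|---|
| Ventilation 1% | 0.8 / 0.4 | 45% / 67% |
| Ventilation 2% | 1.6 / 0.8 | 20% / 45% |
| ICU 1.5% | 1.2 / 0.6 | 30% / 55% |
| ICU 3% | 2.4 / 1.2 | 9% / 30% |
| ICU 5% | 4 / 2 | 2% / 14% |

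**Step 2: a rough hand check.** If the coefficient mainly tracks the share of homes with any event, log IRR ≈ SD × [probit(share, intervention) − probit(share, control)].
- Ventilation 1%, users halved, fitted SD 4.2: 4.2 × (−0.441 − 0.127) = −2.39, so IRR ≈ 0.09. Simulated median 0.08-0.10.
- Set B ventilation, users × 0.7 (1.2 and 0.84 per home), fitted SD 3.8: 3.8 × (0.172 − 0.521) = −1.33, so IRR ≈ 0.27. Simulated median 0.26.

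This heuristic applies only where many homes are at zero. It shows where the number comes from.

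**Step 3: simulated IRR, users halved (true ratio 0.50).** Ranges are across separate simulations.

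| Endpoint | Rate | Median IRR | Ratio of raw totals |
|---|---|---|---|
| Ventilation hours | 0.5% | 0.13 | 0.46 |
| Ventilation hours | 1% | 0.08-0.10 | 0.45-0.52 |
| Ventilation hours | 2% | 0.14-0.15 | 0.48-0.52 |
| ICU days | 1.5% | 0.33-0.36 | 0.43-0.49 |
| ICU days | 3% | 0.38-0.42 | 0.49-0.51 |
| ICU days | 5% | 0.44-0.46 | not tabulated |

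The fitted home SD for ventilation was about 3 to 4.5. In the 600-run set, 95% CI coverage of the true ratio was 78-87% for ventilation and 90-92% for ICU days.

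**Step 4: other effect patterns.**
- Only duration halved, ventilation: median IRR 0.52 to 0.71 across simulations, true 0.50.
- Set B, 30% fewer users: ventilation IRR 0.26 against 0.66 in the simulated data; ICU 0.65 against 0.71.
- Set B, 30% fewer users with proportionally longer use: ventilation IRR 0.32 against 0.94; ICU 0.90 against 1.01.
- Set B, null: IRR near 1, rejection 3-7%.
- An ordinary hospitalisation count: IRR 0.70 against 0.70.

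**Step 5: group means.** Integrating over a normal log-scale intercept multiplies the intercept-at-zero mean by exp(SD²/2).
- Set B ventilation, fewer users: 16 × exp(3.80²/2) = 16 × 1,366 ≈ 21,900 h per 100 (simulated median 21,500). Observed control mean: 181 h.
- Set B ICU, fewer users: 21.3 × exp(0.96²/2) = 21.3 × 1.585 ≈ 34 days per 100. Observed: 30.
- Set A ventilation, 1-2%: 1.5-23 h with the intercept at zero, 3,500-31,000 h integrated, against 68-147 h observed.
- Averaging predictions over the estimated home effects: 65.6 against 65.6 h and 140.4 against 140.4 h observed; ICU 12.7 against 12.8 days.

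**Step 6: region intercept.** A 60-run Laplace fit with region added (Set B) gave a region SD near 0, a ventilation home SD of 3.3-3.7, and integrated means of 8,600-21,500 h against 170 h. Its null median IRR for ventilation was 0.61, against 0.95 in the 300-run fit without region. It is therefore used only for the SDs and means.

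**The case against.** The strongest reply is that the home intercept does a useful job: it takes up the extra variance and keeps the test honest. That stands, since rejection under the null was 3-7%.

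Four stronger readings are tempting, and the documents do not support them.
- **Any halving of ventilation hours would be reported as a reduction of about 85-92%.** This needs the halving to come from fewer ventilated residents. With shorter use by the same number of residents, the IRR is about 0.5 to 0.7.
- **ICU days fail in the same way.** They move towards an ordinary count as use rises: about 0.46 for a true 0.50 at 5% use. The SAP gives no ICU rate, so the size is open.
- **The reported group means must be wrong.** The SAP does not state how the marginal estimators treat the intercept, and averaging over estimated home effects reproduces the raw means. What stands is that the method is unspecified and the choice matters by orders of magnitude for 19. The normal log-scale intercept is likewise a software default, not SAP text.
- **The trial's conclusions are at risk.** Secondary outcomes are explorative (5.1.3), and the key ones are 9e, 10a ii and 10b ii (1.2.2).

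Two further points soften the matter. At 1% use with users halved, the median 95% CI was about 0.003 to 2.1, so the report would usually show how little the estimate says. Artificial ventilation is also analysed as a proportion (endpoint 18), which this mechanism does not affect.

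**Conclusion.** The point holds for endpoint 19 and, more weakly, for endpoint 17. When the effect acts on the number of users, the planned model does not estimate the ratio of hours. Under assumed ventilation rates of 1-2%, a true 0.50 is reported as about 0.1 to 0.15. For ICU days the corresponding figure is about 0.33 at 1.5% use, 0.40 at 3% and 0.46 at 5%. The means per 100 residents for 19 are usable or badly off depending on a method that the SAP leaves open.

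This rests on assumed rates and durations, on the usual normal intercept, and on fits without the baseline covariate. The fault lies in the estimate and the reported means. Type I error is acceptable and the primary analysis is untouched. The change is worth making before analysis but is not critical.

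**What to change.** For endpoint 19, and for 17 if few residents per home have ICU days, replace the random-intercept Poisson model in SAP 5.1.3 with a log-link Poisson working model for the mean:
- Hours or days as outcome, follow-up time as offset, group as a fixed effect. Add region as a fixed effect only where the number of users supports it.
- Standard errors clustered on NH with a small-sample correction.
- Group means per 100 residents taken from this model, with the method stated.
- For 19, the p-value from re-randomising homes within region, in line with the stratification in SAP 2.2.

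Decide from data pooled over both arms whether 17 has few users, so that the choice is not led by the group comparison.

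The cost is a few lines of SAP text and a little programming, with no new data. The downside is that intervals will be wide and may still be slightly too short when few residents are ventilated: coverage was 87-94% for a ratio of totals with NH-clustered errors on t(42). The region-adjusted version and the re-randomisation test were not simulated. At 0.5-2% use with one arm halved there are only 1,760 × 1.5 × rate ≈ 13 to 53 ventilated residents over eight regions, so some regions may have none. That is why region adjustment is conditional.
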